7.5.2 Pharmacokinetic Calculations

The PK parameters (see Table 5) of tepotinib and its metabolites MSC2571109 and MSC2571107, if applicable, will be evaluated. Noncompartmental computation of PK parameters will be performed using the software Phoenix® WinNonlin® 6.4 or higher (Certara, L.P., Princeton, NJ, USA, SAS® System (Version 9.4 or later; SAS Institute, Cary, NC, USA) or equivalent software. Individual PK parameters will be calculated using actual sample collection times. The predose sample time will be considered as if it had been taken simultaneously with the IMP administration. Pharmacokinetic variables will be evaluated and listed for all subjects who provide sufficient concentration-time data.

If AUC_{extra}% is greater than 20%, λ_z and all derived parameters should be flagged as invalid.

Plasma concentrations BLQ before the last quantifiable data point will be taken as zero for calculating the AUC (ie, embedded BLQ values set to zero). Plasma concentrations BLQ after the last quantifiable data point will not be considered for the determination of λ_Z .

 Table 5
 Definition of Pharmacokinetic Parameters

Tepotinib and i	ts Metabolites
Symbol	Definition
AUC _{0-t}	Area under the plasma concentration-time curve (AUC) from time zero to the last sampling time at which the concentration is at or above LLOQ, calculated according to the mixed log linear trapezoidal rule (ie, linear up/log down)
AUC₀-∞	Area under the plasma concentration-time curve from time zero to infinity, calculated as $AUC_{0-t} + AUC_{extra\%}$, according to the mixed log linear trapezoidal rule (ie, linear up/log down). $AUC_{extra\%}$ represents the extrapolated part of $AUC_{0-\infty}$ calculated by $C_{lastcalc}/\lambda_Z$, where $C_{lastcalc}$ is the calculated plasma concentration at the last sampling timepoint at which the measured plasma concentration is at or above LLOQ
C _{max}	Maximum plasma concentration observed
t _{max}	Time to reach the maximum plasma concentration
t _{1/2}	Apparent terminal half-life, calculated as $ln2/\lambda_Z$
λ_{Z}	Apparent terminal rate constant determined from the terminal slope of the log-transformed plasma concentration curve using linear regression on terminal data points of the curve
CL/f	Total body clearance of drug from plasma following oral administration, calculated as $Dose/AUC_{0-\infty}$ (for tepotinib only)
V _Z /f	Apparent volume of distribution during the terminal phase following extravascular administration, calculated as Dose/(AUC _{0-∞*λ_z)}
AUCextra%	Area under the plasma concentration-time curve extrapolated from time t to infinity as a percentage of $AUC_{0-\infty}$
$MRAUC_{0-\infty}$	Metabolite (MSC2571109 or MSC2571107) AUC _{0-∞} to tepotinib AUC _{0-∞} ratio
MRC _{max}	Metabolite (MSC2571109 or MSC2571107) C _{max} to tepotinib C _{max} ratio

7.6 Biomarkers

No biomarker assessments are planned.

7.7 Other Assessments

No other assessments are planned.

8 Statistics

Details of the statistical analyses will be described in a separate statistical analysis plan.

8.1 Sample Size

Pharmacokinetic studies including subjects with impaired hepatic function are usually exploratory by nature. Considering the CVs for the primary endpoints AUC_{0-t} and C_{max} of tepotinib, 20.4% and 22.8% respectively (Study EMR200095-007), 6 evaluable subjects per group will provide 80% power for detecting a group difference of 44% (AUC_{0-t}) and 50% (C_{max}), which is considered

sufficient to meet the study objectives having the therapeutic window of tepotinib in mind. The significance level was set to 0.05 two-sided.

Therefore, 18 subjects (3 groups x 6 subjects) should be included in Part 1 and 6 subjects in Part 2. Drop-outs will be replaced only if they cannot provide an evaluable PK profile.

Randomization 8.2

Not applicable.

8.3 **Endpoints**

8.3.1 **Primary Endpoints**

• PK profile of tepotinib (plasma) in terms of AUC_{0-t}, AUC_{0-∞}, and C_{max} at Day 1 to Day 15 (healthy subjects) or Day 22 (hepatic impaired subjects) calculated by noncompartmental analyses.

8.3.2 **Secondary Endpoints**

• PK profile of tepotinib (plasma) in terms of t_{max}, t_{1/2}, CL/f, V₇/f, AUC_{extra}% at Day 1 to Day 15 (healthy subjects) or Day 22 (hepatic impaired subjects) calculated by noncompartmental analyses

PK profile of the major tepotinib metabolites MSC2571109 and MSC2571107 (plasma) in terms of AUC_{0-t}, AUC_{0-∞}, C_{max}, t_{max}, t_{1/2}, AUC_{extra%} at Day 1 to Day 15 (healthy subjects) or Day 22 (hepatic impaired subjects) calculated by noncompartmental analyses, and MRAUC_{0-∞} and MRC_{max}

• Occurrence of TEAEs, changes from baseline in laboratory safety tests, 12-lead ECG morphology and time intervals (PR, ORS, RR, OT and OTcF), and vital signs.

8.3.3 **Other Endpoints**

Not applicable.

8.4 **Analysis Sets**

Screening Analysis Set

The Screening Analysis Set will include all subjects who provide signed informed consent, regardless of treatment status in the trial. This analysis set will be used for subject disposition.

Safety Analysis Set

The Safety Analysis Set will include all subjects who receive study treatment. All safety analyses will be based on this analysis set.

Pharmacokinetic Analysis Set

The Pharmacokinetic Analysis Set will include all subjects who receive a single dose of the study treatment and have at least 1 postdose PK measurement without important protocol deviations/violations or events (such as vomiting within 2 times the median t_{max}, after dosing) that may affect the PK. All PK analyses will be based on this analysis set.

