 - PK profile of the major tepotinib metabolites MSC2571109 and MSC2571107 (plasma) in terms of AUC_{0-t} , $AUC_{0-\infty}$, C_{max} , t_{max} , $t_{1/2}$, $AUC_{extra\%}$ at Day 1 to Day 15 (healthy subjects) or Day 22 (hepatic impaired subjects) calculated by noncompartmental analyses, and $MRAUC_{0-\infty}$ and MRC_{max}
- Occurrence of treatment-emergent adverse events, changes from baseline in laboratory safety tests, 12-lead electrocardiograms (ECG) morphology and time intervals (PR, QRS, RR, QT and corrected QT intervals using Fridericia's formula [QTcF]), and vital signs.

Pharmacokinetics: Blood samples for PK analysis will be collected on Day 1 predose and 0.25, 0.5, 0.75, 1.0, 1.5, 2.0, 3.0, 4.0, 6.0, 8.0, 10.0, 12.0, and 16.0 hours postdose, Day 2 at 24, 30, and 36 hours postdose, Day 3 at 48, 54, and 60 hours postdose, Day 4 (72 hours), Day 5 (96 hours), Day 6 (120 hours), Day 7 (144 hours), Day 8 (168 hours), Day 10 (216 hours), Day 13 (288 hours), Day 15 (336 hours), and Day 22 (504 hours postdose; hepatic impaired subjects only).

Other assessments: Throughout the study at specified timepoints treatment-emergent adverse events, changes from baseline in laboratory safety tests, 12-lead ECG morphology and time intervals (PR, QRS, RR, QT and QTcF), and vital signs will be assessed.

12/75

Diagnosis and key inclusion and exclusion criteria: Men and women (of nonchildbearing potential), 18 to 75 years (inclusive) of age, with a body mass index of 18 to 36 kg/m² (inclusive) and a body weight \geq 50 kg at Screening, with the absence of acute hepatitis or HIV 1 and 2, who have given informed consent and are willing and able to comply with study procedures will be eligible for enrollment. Subjects with impaired hepatic function (Child-Pugh class A or Child-Pugh class B) and subjects with normal hepatic function will be eligible to enroll in the study. Healthy subjects will be excluded if they have hepatitis B or C or had a previous infection with hepatitis C treated with Sofosbuvir or other antiviral compounds, or any other clinically relevant disease, as considered by the Investigator. Subjects with impaired hepatic function will be excluded if they have primary biliary liver cirrhosis, nonstabilized chronic heart failure, hepatocarcinoma, hepatic encephalopathy (Grade III or IV), sepsis or gastrointestinal bleeding, or any other clinically relevant disease, as considered by the Investigator.

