3.2 Study Rationale

In a mass balance trial, ¹⁴C-MSC2156119 was moderately metabolized in human subjects and a total of 10 different Phase 1 and Phase 2 metabolites were found. Total radioactivity was also mainly eliminated via feces (~78%) while only about 14% was recovered in urine. In feces, roughly 45% of the administered dose could be related to parent drug. This indicates a high extent of active secretion (likely via bile), but unabsorbed drug as well as reduction of N-oxides and hydrolysis of the glucuronide to parent drug may have also contributed to this high recovery. Based on AUC_{all} (which corresponds to the AUC_{0-240h} within the observation period), the M506 could be identified as major metabolite both with respect to European Medicines Agency (EMA) Guidance ICH M3(2) EMA/CPMP/ICH/286/1995 (4) and the draft Food and Drug Administration (FDA) Guidance for Industry – Drug Interaction Studies (5). Ratios of geometric mean values of AUC_{all}

of M506 to total radioactivity and to parent MSC2156119J compound were about 40.4% and 74.9%, respectively. M506 is formed from MSC2156119J with a median t_{max} of 24 hours ranging from 24 to 60 hours and showed an apparent geometric mean half-life of 93 hours ranging from 66 to 145 hours estimated on concentration data from 4 subjects. Urinary excretion was identified as minor route of excretion with an average recovery in urine of only 13.6% (range 8.8% to 17.7%).

According to the hepatic impairment guidances (FDA Guidance for Industry 2003 (9), EMA Guideline CPMP/EWP/2339/02 2005) it should be determined if alterations of excretory and metabolic activities by hepatic impairment can lead to drug accumulation.

Currently, enrolment of subjects into tepotinib HCC studies is restricted to subjects with mild hepatic impairment, ie, Child-Pugh class A.

This study will evaluate the PK and safety of tepotinib in subjects with mild (Child-Pugh class A) and moderate (Child-Pugh class B) hepatic impairment.

In most cases, HCC develops within an established background of chronic liver disease (70 to 90% of all patients) (10) and patients with cirrhosis have the highest risk of developing HCC (90 to 95% of subjects who develop HCC have underlying cirrhosis) (11). It is therefore assumed that the results of this study in subjects with hepatic impairment are also applicable to patients with HCC, especially patients with Child-Pugh class B.

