5.2.3 Rationale for Endpoints

The primary and secondary endpoints are relevant exposure parameters that are required to assess the impact of hepatic impairment on the exposure of tepotinib.

The rationale for including metabolites as secondary endpoints are as follows:

M506 was identified as the only major circulating metabolite and contributes with a low extent to the overall activity. Its contribution to safety and tolerability is not evaluated by nonclinical safety, as tepotinib is developed under the ICH S9 guidance.

M506 is formed from MSC2156119J with a median t_{max} of 24 hours, ranging from 24 to 60 hours, and showed an apparent geometric mean half-life of 93 hours, ranging from 66 to 145 hours, estimated on concentration data from 4 subjects. M506 consists of 2 enantiomers, the S-enantiomer, MSC2571107, and the R-enantiomer, MSC2571109, which have been included as secondary endpoints. MSC2571109 represents the major human plasma metabolite of tepotinib (64.6% of parent AUC_{0-240h}), while MSC2571107 is a metabolite of less significance (4.54% of parent AUC_{0-240h}). A bioanalytical assay is available, which analyzes tepotinib and the enantiomers.

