7.5 Pharmacokinetics

7.5.1 Body Fluids

Blood samples for the PK evaluation of tepotinib and its metabolites (MSC2571109 and MSC2571107) in plasma will be collected at the timepoints specified in the Schedule of Assessments for Part 1 and Part 2 (Table 1). The exact date and time of sample collection will be recorded in the eCRF. Samples not collected at the exact timepoint are not to be considered

47/75

protocol deviations as long as the actual collection date and time is recorded. Every effort should be made to collect samples at the appropriate timepoint.

Details of the sample collection, blood volume, labeling, storage and shipment requirements will be provided in a separate manual of operations or laboratory manual.

The PK sampling is planned differently for healthy subjects than for hepatic impaired subjects as a different half-life is expected. As the majority of healthy subjects do not have measureable concentrations after Day 15, PK sampling until Day 15 is considered sufficient. As the optimal sampling schemes of the hepatic impairment group is difficult to predict, an additional sampling time of 1 week (up to Day 22) is considered to be sufficient. The SMC may decide on a different sampling scheme for Part 2.

All sample analyses will be performed using a validated method measuring parent drug and metabolites.

The free fraction of tepotinib will be determined to assess a potential effect of low serum albumin concentration which might result in an increased free fraction of tepotinib in subjects with hepatic impairment.

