8.5.2 Analysis of Primary Endpoints

As the primary analysis, an analysis of variance (ANOVA) model including hepatic function group as a fixed effect will be applied to log-transformed tepotinib PK parameters AUC_{0-t} , $AUC_{0-\infty}$, and C_{max} of the hepatic impairment groups (Child-Pugh class A and Child-Pugh class B) and matched control group (healthy subjects). Differences between the hepatic impairment groups and matched control will be estimated together with their 90% CIs on the log scale. Point estimates and CIs will be back-transformed to the original scale for presentation.

Additionally, a generalized linear model including hepatic function group and sex (gender) as fixed effects, age and weight as covariates, will be applied to the same primary PK parameters. A further covariate log(dose) will be introduced, when/if Part 2 data is included. The model may be reduced for the final estimates, if appropriate.

All endpoints will be descriptively analyzed using summary statistics by hepatic function group. Graphical displays will be presented, where appropriate.

8.5.3 **Analysis of Secondary Endpoints**

For the secondary PK parameters AUC_{0-t} , $AUC_{0-\infty}$, and C_{max} of the tepotinib metabolites, the same analyses as defined for the primary endpoints will be performed.

In a further analysis, the subjects with liver impairment will be evaluated according to the Albumin-Bilirubin (ALBI) score and the Organ Dysfunction Working Group (ODWG) classification (12.13). Further details of the statistical analyses will be described in a statistical analysis plan.

8.5.4 **Analysis of Safety and Other Endpoints**

Safety data analysis will be conducted on the Safety Analysis Set. The number and percentage of subjects experiencing at least one or more AEs will be summarized by group, relationship to IMP. and severity. Adverse events will be coded using the latest version of the Medical Dictionary for Regulator Activities terminology. Severity of AEs will be graded using the most up-to-date version of the NCI-CTCAE toxicity grades.

Observed and change-from-baseline laboratory values will be summarized by hepatic function group using descriptive statistics, by postdose shifts relative to baseline and data listings of clinically significant abnormalities/outliers, as appropriate.

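### Metabolite AUC0-t runs to 336 h in healthy but up to 504 h in impaired subjects, which can raise the impaired/healthy ratio by about 7-9% with no true effect

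*Protocol*

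**What the plan says.** The Synopsis lists the last PK samples as "Day 15 (336 hours), and Day 22 (504 hours postdose; hepatic impaired subjects only", and section 8.3.2 carries the same split into the metabolite endpoints: "at Day 1 to Day 15 (healthy subjects) or Day 22 (hepatic impaired subjects) calculated by noncompartmental analyses, and". Table 5 in section 7.5.2 defines AUC0-t as the area "from time zero to the last sampling time at which the concentration is at or above LLOQ", with no cut-off time common to the groups. For AUC0-t, AUC0-inf and Cmax "of the tepotinib metabolites, the same analyses as defined for the primary endpoints will be performed" (section 8.5.3), which means log-scale ANOVA by hepatic function group, with impaired/healthy ratios and 90% CIs.

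On the metabolite itself, section 5.2.3 says that M506 "showed an apparent geometric mean half-life of 93 hours, ranging from 66 to 145 hours", estimated in 4 subjects, with a median tmax of 24 h (24-60 h). It adds that "MSC2571109 represents the major human plasma metabolite of tepotinib (64.6% of parent" AUC0-240h), against 4.54% for MSC2571107. Section 7.5.1 justifies the shorter healthy window by stating that "the majority of healthy subjects do not have measureable concentrations after Day 15".

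**The concern.** The length of the AUC0-t window is tied to the group being compared. With a slowly eliminated analyte, some of the area lies between 336 h and 504 h. It can be counted in impaired subjects and cannot be counted in healthy ones. The resulting error goes one way: it raises the impaired/healthy ratio. Read alone, metabolite AUC0-t could then show a small increase produced by the sampling schedule, or partly hide a true decrease such as reduced metabolite formation. The protocol does not discuss this.

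**Working it through.** **Plan's own figure.** The protocol gives no figure for the window effect. Its sample-size statement (section 8.1) does reproduce. A two-sample t-test on the log scale (SD = √ln(1+CV²), n = 6 per group, two-sided 0.05) has power 0.804 for a 44% difference at CV 20.4%, and 0.802 for 50% at CV 22.8%.

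**Inputs.** Last samples at 336 h and 504 h (Synopsis, Table 1). M506 half-life 93 h, range 66-145 h; tmax 24-60 h (section 5.2.3). These are M506 values, not values for one enantiomer. By section 5.2.3, MSC2571109 makes up 64.6/(64.6+4.54) = 93% of the two enantiomers' AUC0-240h, so the result is applied to it. Nothing is claimed for MSC2571107.

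**Model (assumed).** One compartment with first-order formation and elimination, identical in both groups. ke = ln2/half-life, and ka is solved from tmax = ln(ka/ke)/(ka−ke).

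Fraction of AUC0-inf beyond time T: F(T) = [ka·exp(−ke·T) − ke·exp(−ka·T)]/(ka−ke). The second term is negligible here.

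Ratio with no true effect = [1−F(504)]/[1−F(336)].

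**At 93 h.** ke = 0.00745/h. 336/93 = 3.6 half-lives, so exp(−ke·336) = 0.0817; exp(−ke·504) = 0.0234.

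- tmax 24 h: ka = 0.1249/h and ka/(ka−ke) = 1.063. F(336) = 0.087 and F(504) = 0.025. Ratio 0.975/0.913 = 1.068.
- tmax 60 h: ka = 0.0314/h and ka/(ka−ke) = 1.311. F(336) = 0.107 and F(504) = 0.031. Ratio 0.969/0.893 = 1.086.

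Linear-up/log-down trapezoids on the planned sampling times agree to within 0.0002.

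| Half-life | Ratio, tmax 24 / 60 h | C504/Cmax | Extrapolated, healthy | Extrapolated, impaired |
|---|---|---|---|---|
| 66 h | 1.028 / 1.044 | 0.7 / 1.6% | 3.3 / 5.1% | 0.6 / 0.9% |
| 93 h | 1.068 / 1.086 | 3.0 / 4.8% | 8.7 / 10.7% | 2.5 / 3.1% |
| 145 h | 1.144 / 1.163 | 10.4 / 13.6% | 20.7 / 22.8% | 9.3 / 10.2% |

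The 145 h row is weakly supported. Section 3.2 equates the AUC "within the observation period" with AUC0-240h. After a tmax of 24-60 h that leaves (240−24)/145 = 1.5 to (240−60)/145 = 1.2 half-lives.

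**LLOQ.** At 93 h the 504 h sample counts only if the LLOQ is below 3.0% (tmax 24 h) or 4.8% (tmax 60 h) of metabolite Cmax. Otherwise the ratio for that subject is 1.00.

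**Group level.** With half-life log-normal around 93 h (assumed log SD 0.25-0.38), the geometric mean ratio depends on the assumed LLOQ:

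- all subjects quantifiable at 504 h: 1.07-1.09
- LLOQ 5% of Cmax: 1.03-1.07
- LLOQ 10% of Cmax: 1.01-1.04

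**Against the precision.** The 90% CI factor is exp(t(0.95, 15 df)·SD·√(2/6)). At CV 20.4% this is exp(1.753 × 0.202 × 0.577) = 1.23; at an assumed CV of 40% it is 1.48. Coverage of the nominal 90% interval over CV 20.4-40% becomes 84.8-88.6% for a 7% shift, 88.7-89.6% for 3.5% and 89.6-89.9% for 2%.

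**Parent drug.** With an assumed tmax of 8 h, the same calculation for tepotinib gives a ratio of 1.007 at an assumed 48 h half-life, so the primary AUC0-t is little affected.

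**The case against.** The strongest reply uses the protocol's own premise. Section 7.5.1 opens with tepotinib and both metabolites, then says that most healthy subjects have no measurable levels after Day 15. If that covers MSC2571109, then under no true effect most impaired subjects also drop out by then. Setting the LLOQ so that the median 93 h subject falls below it just after 336 h (10.4% or 16.7% of Cmax) leaves a group ratio of only about 1.00-1.02. This stands as a limit on the size. It does not settle the matter, because the sentence names no analyte and fits a 93 h half-life poorly: the modelled Day 15 level is still 10-17% of Cmax.

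Second, AUC0-inf gets the same ANOVA, AUCextra% is reported, the metabolite-to-parent AUC ratio uses AUC0-inf, and no decision rule rests on metabolite AUC0-t. This is largely right. One gap remains. Section 7.5.2 flags λz and all derived parameters as invalid above 20% extrapolation. Near 145 h, healthy subjects would exceed that (21-23%) and impaired subjects would not (9-10%), so AUC0-inf would be weakest in the control group only.

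Third, the longer window is deliberate, to cover a possibly prolonged half-life, and a supportive partial AUC is ordinary SAP material. The first part justifies taking the Day 22 sample, which nobody need remove. On the second, the extra output could indeed be specified in the SAP, which is not at hand; but the unequal windows and the AUC0-t contrast are fixed in the protocol.

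Fourth, the 93 h estimate comes from 4 subjects and from both enantiomers together. That is true, and it is why a range is shown.

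**Conclusion.** The concern holds as a minor point. As planned, metabolite AUC0-t can show an impaired/healthy ratio of up to about 1.07-1.09 at a 93 h half-life with no true difference. The bound is 1.03-1.04 at 66 h and 1.14-1.16 at the weakly supported 145 h. These figures assume one-compartment kinetics, M506 values carried over to MSC2571109, and levels quantifiable at 504 h. Without the last condition the shift shrinks or disappears. It is small beside a 90% CI factor of 1.23-1.48, affects a secondary endpoint in a study the protocol treats as exploratory, and leaves the primary tepotinib comparison essentially untouched.

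**What to change.** In section 8.5.3, keep metabolite AUC0-t and AUC0-inf and add a supportive metabolite AUC0-336h contrast in all groups, defined as AUC to the last quantifiable sample at or before 336 h. State that between-group metabolite exposure is read from AUC0-336h and AUC0-inf together, not from AUC0-t alone. With identical profiles the AUC0-336h ratio is 1.00. Keep the Day 22 sample.

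The cost is one sentence and one output. The Day 15 PK sample is already planned in every group, so no visit or sample is added.

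The drawback is that AUC0-336h understates a truly prolonged tail. With 93 h in healthy subjects, formation rate unchanged and AUC0-inf proportional to half-life, it reads 1.30-1.32 for a true ratio of 1.50 and 1.51-1.54 for a true 2.00. AUC0-t on the protocol's windows reads 1.50-1.52 and about 1.85. AUC0-336h should therefore supplement the two planned AUCs and not replace them.

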8.5 Description of Statistical Analyses

8.5.1 General Considerations

Section 10.6.1 describes the process for performing analyses and reporting of results.

Statistical analysis will be performed using the computer program package SAS System (Version 9.4 or later; SAS Institute, Cary North Carolina, US).

Details on the statistical analysis will be presented in the statistical analysis plan that will be finalized prior to database lock.

The statistical analyses will not be started until all data for Part 1 have been corrected and checked for plausibility and until all necessary coding and assessments have been completed. Part 2 of the study is optional, and if conducted, the results will be provided in an addendum to the CSR.

All data recorded during the study will be presented in individual data listings performed on the Safety Analysis Set, as appropriate.

All data will be evaluated as observed; no imputation method for missing values will be used.

Plasma concentration data will be summarized descriptively for all PK analytes (tepotinib and its metabolites) by hepatic function group and scheduled timepoint using appropriate summary statistics. Any values BLQ will be taken as zero for descriptive statistics.

